Alcohol has multiple biological effects, each of which are potential targets for pharmacotherapy of alcohol use disorder (AUD). Human and animal studies indicate that alcohol-induced generation of GABA_A receptor neuroactive steroid agonists mediates some of alcohol's effects and that chronic alcohol use leads to disturbances in HPA axis function. Dutasteride, a widely used medication to treat benign prostatic hypertrophy, is an inhibitor of 5-alpha reductase (5AR) enzymes, which play a central role in the production of neuroactive steroids as well as in the elimination pathway for cortisol. Thus, dutasteride represents a potential pharmacologic treatment for AUD. Results from the first placebo (pbo)-controlled, randomized study of dutasteride for treating AUD conducted at UConn Health Alcohol Center show that dutasteride 1 mg/day was efficacious in reducing the number of heavy drinking days and drinks per week in treatment-seeking, non-smoking men. During the final 4 weeks of the 12-week treatment phase, 49% of subjects in the dutasteride arm had reduced their drinking by ≥60% compared with 20% of pbo-treated subjects [χ^2 =8.3, p=0.004; OR=3.8 (95% CI=1.5-9.8)] and 33% of subjects in the dutasteride arm had zero heavy drinking days compared with 11% of pbo-treated subjects $[\chi^2=6.7, p=0.01; OR = 4.1 (95\% Cl=2.0-12.5)]$. This treatment response represents a moderate effect size comparable to that observed in a previous study led by [name] and [name] of topiramate for reducing heavy drinking previously conducted at UCONN Health Alcohol Research Center (Kranzler, [name] et al. 2014). We also identified potential predictors of dutasteride treatment efficacy. Subjects with elevated baseline drinking to cope motivation and anxiety showed a greater dutasteride vs. pbo treatment response. This finding suggests that dutasteride may facilitate reduced drinking in part by modulating HPA stress response pathways as hepatic 5α -reductase and 5β -reductase and adipose 5α -reductase are important components of the cortisol elimination pathway. These findings warrant additional study of dutasteride as a new treatment option for AUD. This proposal seeks to extend these findings by:

- **a)** examining the safety, tolerability and efficacy of dutasteride to reduce drinking in a sample including both men and women in a 12-week pbo-controlled, randomized study phase 1;

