Drinking outcomes. Comparison of treatment groups for the modified intention to treat sample (N=135) on the primary outcomes of HDD/week and drinks/ week using generalized linear mixed models (GLMM) showed significant treatment x time interactions (HDD F=9.2; df=1,1406, p=0.002 and SD/wk F=4.8, df=1,1406, p= 0.028). While a minority of our subjects smoke, in view of prior reports of differential medication effects among smokers vs. non-smokers for naltrexone we examined GLMM models that included smoking status, treatment condition, treatment x time, and treatment x smoking as predictors, and identified significant 2-way interactions of treatment x time (F=9.1, df=1,1404, p=0.003 and F=4.4, df=1,1403, p=0.035 for HDD and SD/wk, respectively), and treatment x smoking (F=8.4, df=1,1404, p=0.004 and F=10.9, df=1,1403, p=0.001 for HDD and SD/wk, respectively), such that smokers (n=12) treated with dutasteride drank more throughout the treatment period than smokers treated with pbo (n=12), while the opposite response was observed for non-smokers (dutasteride=56; pbo=55). Smokers and nonsmokers did not differ on baseline drinking, age, Spielberger State Anxiety (SAI) or Beck Depression Inventory (BDI) scores. The interaction of drug x smoking status may relate to the induction by tobacco of phase I metabolism cytochrome P450 and aldo-keto reductase enzymes (Nagaraj, Beckers et al. 2006), the latter of which are involved in neuroactive steroid biosynthesis and metabolism. A prior study showed a positive correlation between serum cotinine levels and the neuroactive steroid allopregnanolone in a sample of 28 men (Marx, Trost et al. 2006). Somewhat surprisingly, with limited exceptions (Fucito, Park et al. 2012, Litten, Ryan et al. 2013, Schacht, Randall et al. 2017) reports for recent RCTs for AUD either did not report the proportion of smokers (Johnson, Ait-Daoud et al. 2003, Johnson, Rosenthal et al. 2007, Johnson, Ait-Daoud et al. 2011, Johnson, Seneviratne et al. 2013, Kranzler, [name] et al. 2014) or did not include smoking status in the analysis of outcomes (Anton, O'Malley et al. 2006, Anton, Myrick et al. 2011, Fertig, Ryan et al. 2012, Litten, Fertig et al. 2012). Interestingly, in the reports by Fucito et al. (Fucito, Park et al. 2012) and Schacht et al. (Schacht, Randall et al. 2017) naltrexone only benefited drinkers who also smoked while our results with dutasteride indicated only non-smokers were responsive, presumably reflecting distinct mechanisms of change. We will include smokers in the proposed study to further evaluate our initial findings. Dutasteride nonresponsive smokers in phase 1 may experience treatment responsive to naltrexone in phase 2 of the proposed study which would support use of smoking as a factor in individualized treatment recommendations.

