
For the majority non-smoker group (n=111) there was a significant interaction of medication group by treatment week (HDD/wk F=6.2, df=1,1183, p=0.013; and SD/wk F=4.7, df=1,1183, p=0.031) **Figure 1**, such that dutasteride treated subjects reduced drinking over time more than placebo subjects. During the last 4 weeks of the 12-week treatment period, the proportion of subjects with a \geq 60% reduction in SD/wk compared with screening (which represents a clinically meaningful reduction from a group average of 48 SDs/wk to less than 20) was significantly greater for the dutasteride vs. the pbo group [49% vs. 20%; χ^2 =8.3, p=0.004; OR=3.8 (95% Cl=1.5-9.8)]. Additionally, among the 91 per protocol completers, during the last month of treatment 33% of subjects in the dutasteride arm had no heavy drinking and 27% no hazardous drinking (no HDDs and no more than 14 SD/wk) compared with 11% and 2% of pbo- treated subjects respectively [no HDD days [χ^2 =6.7, p=0.01; OR = 4.1, NNT=5]; and no hazardous drinking [χ^2 =11.1, p=0.001; OR = 16.4, NNT=4]. The additional analysis described below focuses on the group of 111 non-smokers.

[figure not shown]
Figure 1. Heavy Drinking Days per week (left) and Standard Drinks per week (right) for pbo vs dutasteride treated nonsmokers (mean±SEM).

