comparison in phase 1 and a within-subjects test in phase 2 for patients treated with pbo in phase 1 and dutasteride in phase 2, iii) allow evaluation of whether reductions in drinking are maintained with ongoing treatment for phase 1 dutasteride responders, and iv) provide preliminary data on whether dutasteride non-responders show reductions in drinking when crossed over to naltrexone, an established medication for AUD with a different mechanism of action compared with dutasteride.

Three and six-month follow-up visits following the completion of the 24-week treatment phase will evaluate the durability of treatment effects, allow measurement of the degree to which dutasteride effects on 5AR inhibition have been reversed following 12- or 24-week exposures and to maintain contact with female participants to remind them of the importance of effective contraception for 6 months following treatment.

Table 1. Expected Patient Distribution for Phase 1 and 2.

Phase 1	Phase 1	Phase 1	Phase 2	Phase 2 Statistical contrasts
Treatment	Statistical	Expected Tx	Treatment	
	contrasts	response groups		
Dutasteride n=95 (grp A)	Between-subject contrasts using GLMM Dut vs. Pbo for DVs HDD/wk and SD/wk;.	Dut-R (wk 9-12 Response n=40) Dut-NR (wk 9- 12 Non-Response n=40)	Dut-R dutasteride Dut-NR naltrexone	Within-subject interrupted time series regression using mixed models. Dut-R: Is dut response maintained? Dut-NR: Do dut NRs respond to naltrexone?
	Moderating			
Pbo n=95 (grp B)	effects of genotype, baseline state vs. trait anxiety, perceived stress and interaction with FKBP5 genotype	Pbo-R (wk 9-12 Response n=16) Pbo-NR (wk 9- 12 Non-Response n=64)	Pbo-R pbo Pbo-NR dutasteride	Pbo-R: insufficient sample for statistical comparison. Pbo-NR: Do pbo NRs respond to Dut?

Phase 1 response ≥ 60% reduction SD/wk for wk 9-12 vs baseline (current study 49% response rate for dut vs. 20% pbo). dutasteride 1 mg/day; naltrexone 50 mg/day.

2.C.2. Patients: Drinkers who want to reduce or stop drinking will be recruited using advertisements in radio and print media, by posting/distributing recruitment materials in community settings, informational mailings to area clinicians and by referral from UConn Health medical and dental clinics in at our main campus in Farmington CT together with

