2.C.9.b. Sample size considerations: For Aim 1, the proposed sample size of 160 completing the phase 1 12-week treatment (80 per arm), has 80% power to show statistical significance (α =0.05) for medium-size effects, d=0.4, such as observed in our initial RCT of dutasteride in men (d=0.38 for change in SDs/wk from baseline to last month of treatment comparing dutasteride and pbo n=91]. For Aim 2a, assuming 80% power and α =0.05 and a sample of 40 responder subjects continuing on dutasteride, the non-inferior margin limit would be an increase of 0.67 HDD/wk or 5 SDs/wk during the second 12 weeks dutasteride treatment. For Aim 2b, a sample of 64 placebo non-responders crossing over to dutasteride for phase 2 would have 90% power to detect a medium effect size for reduction in drinking in phase 2 using a within-subjects t-test. For Aim 3, using the GLMPOWER procedure and the between cell effects for the preliminary data presented above (section 2.B.2) for the 2-way interaction of drinking to cope x drug, a sample of 160 subjects in phase 1 would have 80% power to detect the magnitude of this interaction seen in the preliminary dataset.

Table 3. Timeline for recruitment and other study objectives:

Dutasteride AUD#2 protocok V9 (05-18-2022)

IRB NUMBER: 19-147-2 IRB APPROVAL DATE: 02/27/2024

Staff training & study prep										
Patient enrollment & randomizing 5/mo										
3- and 6-month follow-up										
Data entry & cleaning										
Data analysis & Report writing										

Section 3. PROTECTION OF HUMAN SUBJECTS

3.A Risks to Human Subjects

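### The 40 dutasteride responders assumed for Aim 2a come from a non-smoker response rate and allow for no Phase 2 loss, so the stated limit of 5 SD/wk is too favourable

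*Combined protocol and SAP*

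**What the plan says.** The footnote to Table 1 (section 2.C.1) gives the basis of the expected Phase 2 groups as "current study 49% response rate for dut vs. 20% pbo", without saying which patients these rates describe. Applied to 80 Phase 1 completers per arm, they give 40 dutasteride responders and 64 placebo non-responders.

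Two other places identify the source. Section 1 introduces the result by saying that dutasteride "was efficacious in reducing the number of heavy drinking days and drinks per week in treatment-seeking, non-smoking men". Section 2.B.2 reports the two percentages in the paragraph that begins "For the majority non-smoker group (n=111) there was a significant interaction of medication". The same section describes a significant treatment-by-smoking interaction: the 12 smokers on dutasteride drank more than the 12 on placebo, the reverse of what was seen in non-smokers. It then states: "We will include smokers in the proposed study to further evaluate our initial findings".

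Section 2.C.9.b carries the counts forward. For Aim 2a it takes "a sample of 40 responder subjects continuing on dutasteride" and derives a limit of 5 SD/wk or 0.67 HDD/wk at 80% power and alpha 0.05. For Aim 2b it takes 64 placebo non-responders and states 90% power for a medium effect in a within-subjects t-test. It gives no Phase 2 loss, no SD of change, no sidedness, and no number for the Aim 2b effect.

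**The concern.** A response rate from one subgroup is applied to a sample that includes the complementary subgroup, where the protocol's own preliminary data point the other way. The plan also allows for 30 of 190 patients to be lost over the first 12 weeks and for none over the second 12.

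Both choices make the expected number of dutasteride responders larger than the protocol's evidence supports. That number is the direct input to a stated operating figure: how large an increase in drinking Aim 2a could rule out. If fewer than 40 responders contribute, the trial can exclude only a larger relapse than 5 SD/wk, or it excludes 5 SD/wk with less than 80% power.

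**Working it through.** **Inputs from the protocol.** 80 completers per arm; response 49% and 20%; first-trial sample of 135, of whom 24 smoked (24/135 = 17.8%) and 111 did not (82.2%); planned Phase 1 loss 30/190 = 15.8%; Aim 2a limit 5 SD/wk or 0.67 HDD/wk at n=40.

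**Assumptions.** The new trial has the same smoker share as the first. The response rate of smokers on dutasteride is not reported, so I take 0-20%. Phase 2 loss is not stated, so I take the planned Phase 1 loss.

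**Step 1: reproduce Table 1.** 80 × 0.49 = 39.2 (stated as 40). 80 × 0.80 = 64. The counts follow from the rates.

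**Step 2: expected dutasteride responders.**
- Smokers only, response 0%: 80 × 0.822 × 0.49 = 32.2.
- Smokers only, response 20%: 80 × (0.822 × 0.49 + 0.178 × 0.20) = 35.1.
- Phase 2 loss only: 40 × 160/190 = 33.7.
- Both: 32.2 × 160/190 = 27.1, and 35.1 × 160/190 = 29.5.

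**Step 3: Aim 2a limit.** Limit = (z_alpha + z_power) × SD / √n. Without the SD of change, 5 SD/wk cannot be checked independently. It implies an SD of 12.7 at one-sided 0.05, or 11.3 at one-sided 0.025. With the SD held fixed, the limit scales as 5 × √(40/n). The paired-t version, calibrated to give 5 at n=40, is slightly wider. Paired values below are for one-sided 0.05 / 0.025.

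| n | 5 × √(40/n) | Paired-t limit, SD/wk | HDD/wk (× 0.67/5) | Power at 5 SD/wk |
|---|---|---|---|---|
| 40 | 5.00 | 5.00 | 0.67 | 80% |
| 35 | 5.35 | 5.36 / 5.37 | 0.72 | 75% / 74% |
| 34 | 5.42 | 5.44 / 5.45 | 0.73 | 74% / 73% |
| 32 | 5.59 | 5.62 / 5.63 | 0.75 | 72% / 70% |
| 30 | 5.77 | 5.81 / 5.83 | 0.78 | 69% / 67% |
| 27 | 6.09 | 6.14 / 6.17 | 0.82-0.83 | 65% / 62% |

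The loss-only row (n=34) needs no assumption about smokers.

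**Step 4: Aim 2b.** With the same loss, 64 × 160/190 = 53.9, about 54. Power of a paired t-test at alpha 0.05:

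| n | d=0.4 two-sided | d=0.4 one-sided | d=0.5 two-sided |
|---|---|---|---|
| 64 | 88% | 94% | 98% |
| 54 | 82% | 90% | 95% |
| 44 | 74% | 83% | 90% |

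The only numeric value that section 2.C.9.b attaches to a medium effect is d=0.4, under Aim 1. At n=64, exactly 90% two-sided needs d of about 0.41. At n=54 it needs about 0.45 (normal approximation (1.96 + 1.28)/√54 = 0.44).

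**The case against.** Several points on the other side stand.

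- **The counts are expectations and their arithmetic is right.** Table 1 is labelled as expected, and both counts reproduce. The fault is in the inputs.
- **Loss from treatment is not automatically loss of data.** Section 2.C.4.c invites withdrawn subjects to give 24-week drinking data, and the mixed model in section 2.C.9.a.2 can use partial Phase 2 data. Patients entering Phase 2 have already stayed 12 weeks, and the design is meant to help retention, so 15.8% may be too high. Against that, the comparison of the last 4 weeks of each phase needs late data, and drinking recorded after stopping dutasteride does not show that response is maintained on continued treatment.
- **Women may raise the response rate.** Section 2.B.2 expects women to enrich the sample in likely responders. If smokers respond at 20%, a non-smoker rate of (0.49 − 0.178 × 0.20)/0.822 = 55% would restore 49% overall. The protocol gives no such rate.

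A reader might also infer more than the documents support:

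- **That the 90% power for Aim 2b is not delivered.** This holds only if medium means d=0.4 tested two-sided. At d=0.5 power stays at or above 90% down to n=44. The protocol fixes neither the effect nor the sidedness for this aim.
- **That smokers also shrink the 64.** No placebo response rate is reported for smokers. One below 20% would raise the count.
- **That the groups are smaller still because the first trial kept only 107 of 142.** That questions the Phase 1 target of 160 completers, which is a separate matter.

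**Conclusion.** The point holds for Aim 2a. The 49% is a non-smoker rate applied to a mixed sample, no Phase 2 loss is allowed for, and the limit is computed at n=40, above even the 39.2 that the rate gives. Under the stated assumptions the limit becomes about 5.4-5.6 SD/wk from smokers alone, about 5.4 from loss alone, and about 5.8-6.2 from both. With both, power at 5 SD/wk falls to about 65-69% at one-sided 0.05. The erosion is modest and conditional: retained data and enrichment by women could offset part of it, and the missing SD means that the limit can be rescaled but not verified.

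For Aim 2b the finding is narrower. Phase 2 loss lowers power from 88% to about 82% at d=0.4 two-sided; at d=0.5 the 90% claim survives. The statement is incomplete rather than shown to be wrong. The Phase 1 comparison does not depend on any of these figures.

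**What to change.** 1. In the Table 1 footnote, label 49% and 20% as rates in non-smokers.
2. Recompute Table 1 with a stated response rate for the mixed sample and a stated Phase 2 loss allowance, giving the basis for each.
3. In section 2.C.9.b, state the SD of change and the sidedness for Aim 2a, and give the limit as a range. Under the assumptions used here this is about 5.4-6.2 SD/wk, with HDD/wk scaled the same way to about 0.72-0.83.
4. For Aim 2b, state the numeric effect size and sidedness with the power: about 82% at d=0.4 two-sided after loss, or 90% only at a stated larger effect (about d=0.45 at n=54).

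The cost is a revised table and two rewritten sentences. The design does not change and no extra enrolment is needed; the stated precision of the secondary aims becomes somewhat less favourable.

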2.C.2.b. *Inclusion Criteria:* a) men and women age 35 to 70 yo inclusive; b) have an average weekly ethanol consumption of ≥24 SD for men and ≥18 for women and at least 2 HDD/wk over the 8 weeks prior to screening [i.e., substantially in excess of non-hazardous drinking levels (Sanchez-Craig, Wilkinson et al. 1995)]; c) current DSM-5 AUD, d) Have a goal to reduce or stop drinking, e) no evidence of significant cognitive impairment; and f) for women of child-bearing potential (i.e., no hysterectomy, bilateral oophorectomy, or tubal ligation; or <2 years postmenopausal) must be non-lactating, practicing a reliable method of birth control and agree to continue such throughout the study and for 6 months following participation , and have a negative serum pregnancy test prior to initiation of treatment.

We are limiting participation to patients ≥35 yo to minimize the risk to female participants in a phase of life when pregnancy is more common (<35 yo). In our prior studies, only 5% of subjects have been younger than 35. Overall, patients for this study are anticipated to have a moderate level of AUD severity. They will be asked to affirm a

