Dutasteride is contraindicated for use in pregnant women due to the potential effects of dutasteride in utero on the normal development of external male genitalia secondary to reduced fetal DHT (Avodart, Prescribing information 2012, GlaxoSmithKline). As noted in the inclusion criteria and in human subject protections, we will limit participation to women ≥35 who are either not sexually active with men, are practicing effective contraception or are without reproductive capacity. Female participants must have a negative serum β-HCG at study entry and will be monitored every 6 weeks during treatment using urinary HCG. Dutasteride has been safely used off label to treat alopecia (Boersma, Oranje et al. 2014, Seale, Eglini et al. 2016) in pre- and post-menopausal women in clinical practice and pre-menstrual dysphoria in a placebo controlled clinical trial (Martinez, Rubinow et al. 2016). [name] has an IND 74,222 for the study of dutasteride for AUD which includes a protocol including women.

- 2.C.3.b. Naltrexone is FDA approved both as an oral daily treatment (50 mg, Revia) and a long-acting depot IM formulation (Vivitrol) for the treatment of alcohol use disorder. Naltrexone has been shown to reduce heavy drinking in multiple RCTs (Maisel, Blodgett et al. 2013, Jonas, Amick et al. 2014). Naltrexone is an antagonist of the μ-opioid and κ-opioid receptors is thought to reduce alcohol craving and heavy drinking by blocking endogenous opioid induced dopamine release in response to the anticipation of drinking or use of alcohol. Naltrexone will be purchased commercially and over encapsulated using opaque capsules by the UConn Health Research Pharmacy Service. Naltrexone, dutasteride and placebo capsules will be identical in appearance. Subjects assigned to naltrexone in study phase 2 will take 1 capsule of naltrexone 25 mg on phase 2 day 1 and 2 and then 2 capsules each day containing in total 50 mg naltrexone for the remainder of phase 2. All subjects who transition to a different study medication at end of phase 1 will be required to have a negative urine test for opioids and report no opioid use for at least 5 days.
- 2.C.3.c. Pbo drug will consist of lactose powder formulated by the UCONN Health Research Pharmacy Service in gelatin capsules indistinguishable from the capsules containing dutasteride or naltrexone.

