2.C.4.b. Visit 2 (Baseline Visit): 3-21 days after the screening visit, eligible subjects will return for their baseline visit. Subjects will be instructed in the use of study medication and will take one capsule study medication (0.5 mg dutasteride or pbo) at the baseline visit and again on study day 2, followed by 2 capsules daily for the remainder of the phase 1 12-week treatment period (in order to match capsule number for 2 day naltrexone titration in phase 2). Finally, subjects will be trained to use a paper calendar provided by staff to record their daily drinking and use of the IVR system to record their mood, desire to drink, self-efficacy and daily drinking during weeks 1-4 and 9-12 of phase 1 and 21-24 of phase 2. We considered asking subjects to use the IVR report daily for the 168 days of treatment but considered that this would be an excessive subject burden.

Study visits beyond visit 2, may be conducted remotely by telephone if a participant is unable to come to the clinic due to illness, travel, or other valid concerns (e.g. about exposure to COVID-19) related to traveling to UConn Health. Participants will be sent a one-time use REDCap secure link via email to complete study visit surveys. In the event a

participant is unable to attend an in person scheduled visit, backup supply of medication previously provided may be used or additional medication (up to 8 weeks) will be provided at an earlier visit if inability to attend future scheduled visit is anticipated in advance. Study staff will consult with study physician regarding whether study medication should be continued if a participant reports illness as reason for a missed in person visit. All unused medications will be brought to the next in person study visit.

2.C.4.c. Bi-weekly Clinic or remote Visits 3-14: A brief Timeline Follow-Back (TLFB) interview will be performed to track participants' daily alcohol consumption and medication use since the last study visit, and a trained staff member will deliver the medical management intervention.

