2.C.6.a. Laboratory/Medical Assessments: A physical examination, urinalysis, urine toxicology, serum bHCG (for women), CBC, and a chemistry panel (which includes electrolytes, liver enzymes [ASAT, ALAT, GGT], direct bilirubin, BUN, and creatinine) will be used to screen subjects for medical exclusion criteria. ASAT, ALAT will be repeated for subjects with elevations at baseline greater than 3x normal at weeks 6, 12, 18 and 24 (or until reduced to less than 3x normal). Weight, blood pressure and pulse will be obtained at each treatment visit. Urine will be tested every 6 weeks for drugs of abuse and HCG for women of reproductive potential. Blood will be archived for measurement of phosphatidylethanol (PEth) by a commercial testing lab as an objective measure of alcohol use. PEth is an alcohol-specific adduct catalyzed by phospholipase D from ethanol and phosphatidylcholine in membranes of red blood cells and is not affected by liver or kidney disease, age or sex. It is a sensitive and specific metabolite which is produced in direct response to use of alcohol during the past 20-30 days (Viel, Boscolo-Berto et al. 2012). PEth levels are correlated with the amount of alcohol consumed (Aradottir, Asanovska et al. 2006) and correlate better with daily diary drinking reports than carbohydrate deficient transferrin or gamma glutamyl transferase (de Bejczy, Lof et al. 2015, Walther, de Bejczy et al. 2015). Blood for PEth will be collected at screening, and weeks 6, 12, 18 and 24. Serum 3α-diolG will be measured using a commercial ELISA kit as a biochemical measure of 5AR inhibition by dutasteride. 3α -diolG is a major metabolite of testosterone and is more abundant that DHT especially in women and has been shown to decrease in parallel

with DHT following finasteride treatment in men (Rittmaster, Stoner et al. 1989, Gormley, Stoner et al. 1990) and has been used to monitor the reduction of 5AR activity in women treated with finasteride (Wong, Morris et al. 1995, Falsetti, Gambera et al. 1999). Serum testosterone, estradiol, progesterone, cortisol, ACTH and sex hormone binding globulin will be measured using commercial immunoassays to evaluate changes in these steroid hormones during treatment with dutasteride. Blood for 3α -diolG and steroid hormones will be collected at screening and weeks 6, 12, 18 and 24.

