Study Visit	V1 Screen	V2 Baseline	V 3-7	phase 2 baseline	V 9-13	V14	V15-16
Time relative to Medication		Start medication	wks 2, 4,6,8,10	wk 12 end phase 1	wks 14, 16,18,20,22	wk 24 end phase 2	3- and 6- mo follow- up
Medical History, demographics, AUDIT, SCID, FHAM, ACES, TESI, STAI-trait, Clinical screening labs, blood for DNA and research analytes Physical Exam & Clinician review of Medical History	x						

TLFB, PHQ-9, CIWA, MTR	X	Х	X	X	Χ	X	Χ
Vital signs & weight	Х	Х	X	Х	Х	Х	Х
DMQ, AEQ, SIP	Х			Х		Х	Х
Study outcome blood samples	Х		wk 6	Х	wk 18	Х	Χ
Urine drug screen, HCG (women), PACS	Х		wk 6	Х	wk 18	Х	Х
STAI-state, PSS		Х					
STAI-trait, PSS				Х		Х	Х
Daily IVR call		Х	wk 1-4	wk 9-12		wk 21-24	
Side Effect Checklist (SAFTEE)		Х	Х	Х	Х	Х	Х
Medical Management		Х	Х	Х	Х	Х	
Alcohol SCID past 1 month				Х		Х	Х

The IVR system will use the same procedures we have used in the recently completed dutasteride study and prior UConn Health studies of topiramate (Kranzler, Armeli et al. 2016). a) Daily drinking diary: Every evening, as part of the IVR daily diary, patients will record their alcohol consumption as the number of standard drinks in each of three categories of alcoholic beverages: beer, wine, liquor. Patients are asked to report separately drinking from yesterday and any drinking during the current day, up until the time of the IVR report. This allows us to examine lagged associations with mood and life event triggers. b) Daily mood: Patients will be asked to rate as part of the daily IVR their mood using an adjective checklist. The checklist consists of 9 adjectives (Larsen and Diener 1992) with each rated on a 5-point scale (0 = "not at all" to 4 = "extremely"). Three adjectives for each of three mood state dimensions provide measures of positive mood, negative mood and activated mood. Subjects will also be asked to report their self-efficacy for managing life problems. c) Daily Events: Participants will be asked whether they experienced a list of nine possible daily events (3 stressful, 3 pleasant, and 3 situations where someone might drink). These measures will be used to assess the influence of positive and negative current life events on drinking. d) Drinking motives: Participants will be asked to respond to 3-items for each of three drinking motives as to why they drank today and yesterday; to cope, to enhance or to socialize on a 3-point scale (1= "not at all", 2="somewhat" and 3="definitely).

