
Procedures to minimize potential exposure of pregnant women to active study medication (dutasteride or naltrexone) include 1) excluding subjects younger than 35 who may have a greater likelihood of considering pregnancy after starting the study and would need to avoid pregnancy for 6 months following treatment with dutasteride, 2) inclusion requirement of a negative serum bHCG at screening together with monitoring of urine HCG during the 24-week treatment, 3) review of teratogenic risks by study physician with female subjects, 4) agreement by women of reproductive potential to use effective contraception during the study and for 6 months following completion of medication use, 5) monthly contact by study nurse during 6 month follow-up to remind women of importance

of effective contraception. If a patient reports being pregnant or tests positive, she will be immediately withdrawn from study medication treatment, referred for obstetric evaluation, informed as to the study medication she had taken and advised to discontinue drinking alcohol.

Confidentiality: To avoid breach of confidentiality, patients' names will appear only on a consent form, a telephone screening form, the study nurses visit contact information sheet and a "key" form kept by study staff in a locked cabinet. All forms that contain identifying information will be kept double locked (i.e., in a locked cabinet, in a locked room) to maintain their security. All study data forms will contain only the patient's unique study identification number. Prior to final study closure, any links between personal identifiers and each subject's unique study ID will be deleted to generate a de-identified dataset. Patient visits will be scheduled by study staff and no information about the patient will be provided to anyone outside the study team (except in emergencies as defined above) in person or by telephone, except as required by law. The study will be conducted in an outpatient clinic in which treatment is provided to patients who have a variety of problems, not limited to substance abuse. To further help protect participant privacy, a Certificate of Confidentiality from the National Institutes of Health will be in force for this study. This certificate will protect the investigator and immediate study staff from being forced to release any research data that would identify a participant in this study, even under a court order or subpoena.

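### No pregnancy test is scheduled at V2, so the first dutasteride capsule can follow the only pre-dose testing occasion by 3 to 21 days; a urine HCG at V2 would close this gap cheaply, though its expected yield is low

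*Combined protocol and SAP*

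**What the plan says.** Section 2.C.3.a states the hazard: "Dutasteride is contraindicated for use in pregnant women", because lower fetal DHT may affect development of the male external genitalia.

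The pre-dose test is described in four places, which agree.

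- Section 2.C.2.b requires that women of child-bearing potential "have a negative serum pregnancy test prior to initiation of treatment". It sets no maximum interval between test and dose.
- Section 2.C.6.a puts the serum test in the screening panel.
- Section 3.B.1 lists as a safeguard the "inclusion requirement of a negative serum bHCG at screening together with monitoring of urine HCG during the 24-week treatment".
- Section 2.C.3.a asks for a negative serum result "at study entry and will be monitored every 6 weeks during treatment using urinary HCG".

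On timing of the first dose, Section 2.C.4.b says that "3-21 days after the screening visit, eligible subjects will return for their baseline visit" and that they "will take one capsule study medication (0.5 mg dutasteride or pbo) at the baseline visit".

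For testing on treatment, Section 2.C.6.a says "Urine will be tested every 6 weeks for drugs of abuse and HCG for women of reproductive potential". In Table 2 (Schedule of Assessments) the row "Urine drug screen, HCG (women), PACS" is filled at V1, week 6, week 12, week 18, week 24 and the follow-up visits. It is blank at V2.

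**The concern.** The V1 result satisfies the entry rule even when V2 falls three weeks later. A woman who conceives after the V1 test, or too shortly before it to test positive, can take her first capsule without the protocol prompting another test. The next scheduled test comes after 42 days of dosing.

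What is at stake is fetal exposure in a small number of participants, not any estimate in the trial. Two statements in the plan make it better to prevent the first dose than to detect the pregnancy later. Section 2.C.3.a expects DHT to have fallen by about 80% by week 4, which is before the week-6 test. Women must also continue contraception for 6 months after treatment, so stopping the capsules does not end exposure at once.

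The schedule treats the two routes to dutasteride differently. Women who start it at week 12 as placebo non-responders have an HCG marked at that visit. Women randomised to it at V2 do not.

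**Working it through.** The plan gives no figure of its own to reproduce. The check is a comparison of the schedule with the text, followed by date arithmetic.

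**Inputs from the protocol**
- Gap g from V1 to V2: 3 to 21 days (Section 2.C.4.b).
- First HCG on treatment: week 6, or 42 days (Table 2, Schedule of Assessments).
- Randomised: 190, with 95 to dutasteride in phase 1 (Table 1).
- Anticipated share of women: 35% (Section 2.C.2).

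**Assumptions (not in the protocol)**
- 25 to 75% of the women are of reproductive potential.
- 1 to 10% conceptions per woman-year on contraception.
- A test turns positive L = 8 to 14 days after conception, the same for serum and urine.

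**1. Test intervals**

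| | Now | With an HCG at V2 |
|---|---|---|
| Last test to first dose | 3 to 21 days | 0 days |
| Test to test across the first dose | 3 + 42 = 45 to 21 + 42 = 63 days | 0 + 42 = 42 days |
| First dose to next scheduled test | 42 days | 42 days |

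**2. Women exposed from V2**
- All women on phase 1 dutasteride: 0.35 × 95 = 33.25, about 33.
- Of reproductive potential: 33.25 × 0.25 = 8.3 to 33.25 × 0.75 = 24.9, so about 8 to 25.

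**3. Pregnancies that a V2 test would catch**
- Now, conceptions in the last L + g days before V2 are undetected at first dose: 8 + 3 = 11 to 14 + 21 = 35 days.
- With a V2 test, only the last L days are undetected: 8 to 14 days.
- The window removed is therefore g days long, whatever L is. As a share of the undetected window, g/(L + g):
  - g = 3: 3/17 = 18% to 3/11 = 27%.
  - g = 21: 21/35 = 60% to 21/29 = 72%.

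**4. First-dose exposures prevented in the whole trial**
- Women × g/365 × conception rate.
- Low end: 8.3 × 3/365 × 0.01 = 0.0007.
- High end: 24.9 × 21/365 × 0.10 = 0.14.

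**5. When the caught pregnancies began**
- They were conceived between L + g and L days before V2, and V1 itself lies g days before V2. So max(0, g − L) of the g days fall after V1.
- g = 3: none. Every pregnancy caught began before V1 and was not yet detectable there.
- g = 21: 21 − 14 = 7 to 21 − 8 = 13 of 21 days, or 33 to 62%. The rest began before V1.

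The figure in step 4 therefore counts exposures prevented. It happens to equal the expected number of conceptions between V1 and V2, but these are largely different pregnancies. If urine turns positive later than serum, the yield is smaller.

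**The case against.** The strongest case against is that the plan is internally consistent and already layers its safeguards. Women must be 35 or over. Section 2.C.3.a limits entry to those not sexually active with men, using effective contraception, or without reproductive capacity. A study physician meets each subject at the start of treatment (Section 2.C.5) and reviews teratogenic risk with women (Section 3.B.1). Study drug stops on a reported pregnancy or a positive test. Against this, the expected yield stays well below one event even at the worst-case end. The described harm concerns a male fetus; if half are male, the yield halves again, to about 0.0003 to 0.07.

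All of this stands, and it limits how strongly the point can be put. It does not remove the point, because none of these measures is a test at first dose, and the plan itself adds HCG testing on top of them.

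A reader might infer three stronger things that the documents do not support.

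- **That an undetected pregnancy would be exposed for a full 42 days.** This is a ceiling. Section 2.C.6.b.4 has the time since last menses collected at each treatment visit, partly for safety monitoring, and visits fall at weeks 2 and 4. A late period could bring the pregnancy to light sooner, although no rule ties that answer to an HCG or to holding the dose.
- **That there is only a single negative result before dosing.** Table 2 also marks the urine row at V1, so serum and urine may both be done. What is single is the testing occasion.
- **That remote visits let the 6-weekly HCG lapse.** Section 2.C.4.b allows telephone visits after V2 and up to 8 weeks of extra capsules, but it does not waive the testing required by Sections 2.C.3.a and 2.C.6.a. How a due test is obtained then is unstated detail, not a shown gap. Limiting capsule supply on that account could interrupt dosing in women only, in a trial that hypothesises larger effects in women.

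**Conclusion.** The gap is real. The table and the text agree that no pregnancy test is scheduled between V1 and week 6, so the first dose can come 3 to 21 days after the only pre-dose testing occasion. The V2 cell is blank while the rest of the HCG row is filled, and the text matches, so a table-reading fault is unlikely.

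The size is small: about 0.0007 to 0.14 first-dose exposures prevented over the trial, given the assumed proportion of reproductive potential, conception rate and detection lag. The upper end also takes every gap to be 21 days. A V2 test leaves conceptions in roughly the last 8 to 14 days undetected, and for those the time to the next scheduled test is unchanged. No efficacy estimate is affected.

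The change is worth making because it is very cheap, the drug is contraindicated in pregnancy, and the schedule already has a test at the other visit where dutasteride is started. It is a low-yield safety improvement, not the correction of an error.

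**What to change.** In Table 2 (Schedule of Assessments), add a urine HCG at V2 for women of reproductive potential, read as negative before the first capsule is taken. Do this in both arms so that the blind is kept. Keep the week-6 test, since the V2 test cannot detect the most recent conceptions. Leave the action on a positive test as Section 3.B.1 has it.

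V2 is an in-person visit, because Section 2.C.4.b allows remote visits only after it, so the result can be read in the clinic.

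The cost is at most 0.35 × 190 = 66.5, about 67 urine strips. If 25 to 75% of the women are of reproductive potential, it is about 17 to 50 (66.5 × 0.25 = 16.6; 66.5 × 0.75 = 49.9). Add a few minutes at V2 and one mark in the table. No extra visit is needed, and the sample size and analyses stay as they are.
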